3.1.2 Randomized treatment epoch (Epoch 2)

3.1.2.1 Randomization

At baseline, eligible patients will be randomized in a ratio of 1:1 within each cohort to one of below 2 treatment arms:

- Canakinumab 150 mg (or 2 mg/kg for patients weighing ≤ 40 kg) every 4 weeks (q4w)
- Placebo

Patients from the non-randomized group will enroll to the open label arm of canakinumab 150 mg (or 2 mg/kg for patients weighing ≤ 40 kg) every 4 weeks (q4w). They will be eligible for add-on injection and up-titration as described in the following sections but always receive open label medication.

All patients will receive the first subcutaneous injection at Baseline and will return to the site every 4 weeks to receive additional injections of investigational treatment for 16 weeks.

The resolution of the index flare will be assessed at Day 15. Resolution of the index flare is defined as PGA <2 (“minimal” or “none”), **and** CRP within normal range (≤ 10 mg/L) or reduction by at least 70% from baseline. Patients whose index flare has resolved will not be up-titrated. If their index flare has not resolved by Day 15, they will be eligible for blinded escape (see [Section 3.1.2.2](#)).

Visits to assess efficacy and safety are scheduled at Day 15, Day 29 and subsequently at 4 weeks intervals during the randomized treatment epoch. Patients might receive an up-titration if they have persistent disease activity or they re-flare before Day 29 (see [Section 3.1.2.2](#)) or after Day 29 (see [Section 3.1.2.3](#)).

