3.1.3 Randomized withdrawal epoch (Epoch 3)

3.1.3.1 Re-randomization

All patients randomized to placebo at baseline and completing the randomized treatment epoch (Epoch 2) without any re-flare will be considered placebo-responders. To avoid exposure to canakinumab which may not be justified in light of the clinical status, these patients will be withdrawn from the study treatment.

Patients who initiated blinded escape or entered the open-label treatment arm in the randomized treatment epoch (Epoch 2), non-randomized cohort patients and roll-over TRAPS patients will not be re-randomized and will enter the open-label treatment arm in Epoch 3; for patient management details refer to [Section 3.1.3.2](#).

All patients randomized to canakinumab 150 mg (or 2 mg/kg for patients weighing ≤ 40 kg) q4w at baseline and completing the randomized treatment epoch (Epoch 2) who did not require blinded escape or to enter the open-label treatment arm will be re-randomized in a ratio of 1:1 to:

- Canakinumab 150 mg (or 2 mg/kg for patients weighing ≤ 40 kg) q8w
- Placebo

Re-randomized patients will receive the first s.c. injection on Day 113 and will return to the site every 8 weeks to receive additional injections of investigational treatment for 24 weeks.

Visits to assess efficacy and safety are scheduled at 8 weeks intervals during the randomized withdrawal epoch (Epoch 3). Patients might receive an up-titration if they re-flare at unscheduled visits (see [Section 3.1.3.2](#)).

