3.1.4 Open-label treatment epoch (Epoch 4)

All patients who were re-randomized to placebo on Day 113 but completed the randomized withdrawal epoch (Epoch 3) without re-flare will enter Epoch 4. They will present for scheduled visits but will not receive any investigational drug. In case they re-flare, they will enter the open-label treatment arm receiving canakinumab 150 mg (or 2 mg/kg for patients weighing ≤ 40 kg) q8w. In case of experiencing a flare, up-titration will be allowed as specified in Section 3.1.3.2.

All other patients will enter the long-term safety open-label treatment epoch of 72 weeks duration. They will continue on their last dosing regimen as administered during the randomized withdrawal epoch (Epoch 3). Visits to assess efficacy and safety are scheduled at 8 weeks intervals during the open-label treatment epoch (Epoch 4).

In case of re-flares (PGA ≥ 2 and CRP ≥ 30 mg/L) before the next scheduled visit, (step-wise) up-titration up to a dosing regimen of canakinumab 300 mg (or 4 mg/kg for patients weighing ≤ 40 kg) q4w will be allowed. The same principles for up-titration as outlined in [Section 3.1.2.3](#) or [Section 3.1.3.2](#) will apply.

No down-titration will be allowed during Epoch 4.

Visits to assess efficacy and safety are scheduled at 8 weeks intervals during the open-label treatment epoch (Epoch 4). Patients might receive an up-titration if they re-flare during Epoch 4. Patients up-titrated to q4w administration will come back every 4 weeks for unscheduled visits at Day 309, Day 365, Day 421, Day 477, Day 533, Day 589, Day 645, Day 701 and Day 757 in addition to the visits scheduled defined in Table 6-2.

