5.5.6 Rescue medication

Increase of corticosteroid maintenance dose or intermittent steroid treatment up to the dose detailed in [Table 5-1](#) may be used as rescue therapy.

Standard doses of NSAIDs can be used from Day 15 inclusive on an as needed basis to treat the sign and symptoms of TRAPS, HIDS or crFMF during acute flares at the discretion of the investigator. Before Day 15, NSAIDs should not be used for treating any signs or symptoms of the index flare.

Use of rescue medication must be recorded on the concomitant medications page in the CRF.

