Patients needing dose escalation in the canakinumab arms, or who escape from placebo arms to canakinumab in the randomized treatment epoch (Epoch 2) or discontinued from the study due to any reason prior evaluating the endpoint at week 16, will be considered as having PGA ≥ 1 and PPGA ≥ 1 . Patient/parent's global assessment of disease activity (PPGA) will also be summarized for weekly averages using summary statistics. Week 0 will be average of PPGA score from day -7 to day 1, week 1 will be average of score from day 2 to day 7, week 2 will be average of score from day 8 to day 14 and so on.

In addition, Spaghetti plot will be provided by subject and cohort and initial randomized treatment for PGA assessment and Physician's severity assessment of disease signs and symptoms

In the final analysis, shifts in PGA score from baseline to end of Epoch 4 by treatment group for each cohort will be shown in figures. , Summary tables of PGA after patients taking ACZ885 will be shown by visit, from Baseline to last visit in Epoch 4.

Episodes of Fever

Number and duration of fever episodes collected in patient's diaries will be summarized within each cohort, epoch and treatment group (as defined in [section 1.3](#)). Plots of fever episodes per patient over time (displaying frequency and duration) and treatment group will also be presented. Treatment difference for time to first resolution of fever will be analyzed using a Cox proportional hazard regression model. The Kaplan-Meier estimates of the proportion of patients with first resolution of fever along with the associated 95% confidence intervals using the Greenwood's formula will be provided.

Rescue medication

Corticosteroids levels will be summarized descriptively by analysis visit for each cohort and by treatment group (as defined in [section 1.3](#)). In addition, the number and percentage of patients who reduce their corticosteroids maintenance dose at Week 16 compared to baseline, patients who take corticosteroids rescue medication and patients who take only NSAIDs rescue medication during the study, patients who take steroid level >0.2 mg/kg/day will also be presented. Between-treatment differences for the proportion of patients who are able to reduce their corticosteroids at Week 16 will be analyzed using a Fisher's exact test for each cohort. The analysis will only include subjects who were receiving corticosteroids at baseline.

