Rescue medications are not collected visit wise in the study and are collected in summary page as part of concomitant medications. Rescue medications will be mapped to visits. Rescue medications shall be assigned to visit based on start and end date of the medication and corresponding visit date. For example, if visit date for visit 103 lies between start and end date of "VALISONE-G" corticosteroid then dose level of this concomitant medication will be assigned to visit 103. If there are more than one dose that are assigned to same visit then these

doses shall be added after converting the units to mg/kg/day. If there are no records of rescue medication for any visit then it shall be considered as 0 mg/kg/day dose.

Blinded escape

The number and percentage of patients who require blinded escape from Days 8 to 28 will be summarized by cohort and randomized treatment group.

Auto-Inflammatory Disease Activity Index (AIDAI)

Symptoms evaluated in the AIDAI diary will be summarized with each cohort and epoch (2 and 3) and by treatment group (as defined in [section 1.3](#)) for monthly score as sum of scores over a month. Spaghetti plot will be provided by subject and cohort and initial randomized treatment.

Time to first new flare in the randomized withdrawal epoch (Epoch 3)

Time to first new flare in Epoch 3 will be analyzed for patients re-randomized at the start of epoch 3. The two treatment groups (150mg q8w and placebo) will be compared using a one-sided log-rank test at the 2.5% significance level. The hazard ratio and its associated 95% two-sided confidence intervals will be estimated. Kaplan-Meier estimates of the probability to experience a flare event will be calculated from the start of the randomized withdrawal epoch. 95% confidence intervals using Greenwood's formula will be provided.

Patients who discontinued the study in epoch 3, or having an up-titration or escape from placebo group to canakinumab arm will be counted as having a flare in epoch 3. In this case the date of the premature subject withdrawal (PSW) visit, or resp. time of up-titration or escape is considered as the end date for the calculation of time to flare.

SF-12 Health Survey (SF-12)

SF-12 scores will be summarized (descriptively) by epoch (2 and 3), analysis visit, initial randomized treatment and treatment sequence (as defined in [section 1.3](#)) within each cohort. Only patients ≥ 18 years of age at baseline will be part of the analyses.

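### The by-visit steroid summaries do not show rescue courses that start and end between visits; interval summaries from the dates already recorded would restore them

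*SAP*

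**What the plan says.** Rescue by steroid can take two forms under Protocol 5.5.6: "Increase of corticosteroid maintenance dose or intermittent steroid treatment", up to a stated dose.

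On collection, SAP 1.10.5 says: "Rescue medications are not collected visit wise in the study and are collected in summary page as part of concomitant medications". Courses are then mapped to visits by date. The SAP's example assigns a dose to Visit 103 "if visit date for visit 103 lies between start and end date of" the course. Several doses that map to one visit are converted to mg/kg/day and added. For everything else the rule is: "If there are no records of rescue medication for any visit then it shall be considered as 0 mg/kg/day dose".

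The mapped doses feed this output: "Corticosteroids levels will be summarized descriptively by analysis visit for each cohort and by treatment group", with groups as defined in SAP 1.3. The same SAP paragraph also plans counts of patients with any steroid rescue during the study, and a Week 16 comparison of the proportion who reduced their steroid, limited to patients on steroid at baseline. SAP 1.9 summarises rescue medication by cohort, epoch, initial randomised treatment, treatment sequence and ATC class.

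The objectives served are in Protocol 2.3: the use of rescue medication over time, and the proportion able to lower their maintenance steroid by the end of each epoch.

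**The concern.** The rule reads an intermittent drug only on visit days. No rule carries a course lying wholly between two visits to either visit, for instance as a maximum, a mean or a yes/no flag since the last visit. Visits are 14 to 28 days apart in Epoch 2 and 56 days apart in Epochs 3 and 4, so a short course can easily fall in a gap.

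The by-visit table is the planned output that shows steroid use over time within an epoch. If it leaves out most short courses, it cannot show how many patients needed rescue in a given interval, or when.

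A second, separate weakness lies in the same paragraph. Adding all doses mapped to a visit mixes maintenance with rescue, and the Week 16 reduction analysis is meant to concern maintenance.

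**Working it through.** The documents state no figure on this point, so there is nothing to reproduce.

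**Inputs**
- Epoch 2 visits (Protocol Table 6-1): Days 1, 15, 29, 57, 85, 113, giving gaps of 14, 14, 28, 28, 28 days.
- Epochs 3 and 4 (Protocol 3.1.3.1, 3.1.4): 56-day gaps. SAP Table 2-1 also lists 28-day analysis visits in Epoch 3, and patients up-titrated to q4w in Epoch 4 have extra visits that make their spacing 28 days.
- Course length L: not given, so **assumed** to be 1 to 7 days. The only duration guide is the crFMF eligibility flare of roughly 12 to 72 hours (Protocol 4.1.4), and that describes a flare, not a steroid course.
- Start day: **assumed** unrelated to visits, that is, uniform.

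**Share of courses that touch a scheduled visit**

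A course of L days covers a visit if start ≤ visit ≤ end. For one gap of G days with L ≤ G, the share is L/G. For Epoch 2 as a whole, starts on Days 2 to 113 give 112 possible days and 5 visits, so for L ≤ 14 the share is 5L/112.

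| L (days) | Epoch 2, 5L/112 | 28-day gap, L/28 | 56-day gap, L/56 |
|---|---|---|---|
| 1 | 4.5% | 3.6% | 1.8% |
| 3 | 13.4% | 10.7% | 5.4% |
| 5 | 22.3% | 17.9% | 8.9% |
| 7 | 31.2% | 25.0% | 12.5% |

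The share missed is 100% minus these values: about 69% to 96% in Epoch 2, and 87.5% to 98.2% at 56-day spacing.

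**How far this depends on the assumptions**
- *Length.* More than half are missed while L/G < 0.5: up to 6 days for a 14-day gap, 13 days for 28 and 27 days for 56. Over Epoch 2 as a whole, a 10-day course is captured 44.6% of the time and a 14-day course 62.5%.
- *Start of the period.* Counting only starts from Day 16 (4 visits, 98 days), a 7-day course is captured 4 × 7/98 = 28.6% of the time.
- *Reading of the rule.* If start and end dates do not count as inside the course, capture falls. A 3-day course in Epoch 2 goes from 13.4% to 5 × 1/112 = 4.5%.
- *Timing.* Suppose a fraction f of courses starts on a visit day and is always captured. With c the share from the table, half are captured when f = (0.5 − c)/(1 − c). For 3-day courses f is 42% (Epoch 2) to 47% (56-day gap); for 7-day courses it is 27% to 43%.

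**Is the mean dose biased?**

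Take a 5-day course at 0.2 mg/kg/day in a 28-day interval. The expected visit-day dose is 0.2 × 5/28 = 0.0357. The interval average is (5 × 0.2)/28 = 0.0357. They are equal: a course is seen rarely, but then at full dose. A simulation over Epoch 2 agrees (0.0086 by both methods).

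**What is lost**

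Assume, for illustration, that 40% of a group of 30 with no maintenance steroid take one 5-day course in a 28-day interval. Then 12 patients were treated, but about 12 × 5/28 = 2.1 (7%) show a dose at the visit. The SAP's standard summary statistics (SAP 1.1) include quartiles. With about 2 of 30 above zero, the upper quartile of the visit-day dose is zero. With 12 of 30 above zero, the upper quartile of the interval dose is not.

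**Week 16 reduction analysis**

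Patients must be in a flare at randomisation (Protocol 4.1.2 to 4.1.4). The SAP does not say whether this analysis uses the mapped, summed doses. If it does, an intermittent course covering Day 1 raises the baseline dose and its later absence reads as a reduction. A rescue course covering Day 113 is added to the maintenance dose and can mask a true reduction.

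**The case against.** The strongest reply is that the table is a legitimate point-in-time summary. Zero is the true rescue dose on a visit day outside any course, and under random timing the mean is unbiased. The number of patients who ever took steroid rescue, and the by-epoch summary by randomised treatment, are not described as depending on a visit-day match, so the rescue objective does not rest on this table alone. No primary or secondary test uses the mapping. All of this stands, and it limits the point to occurrence and timing within an epoch.

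Capture is also better than the table in three situations. Protocol 3.1.2.2 directs rescue from Day 15 until Day 29 dosing in patients not improving after the add-on injection, and continuous steroid use over that period would touch visits. The 14-day gaps early in Epoch 2 catch 3/14 = 21% to 7/14 = 50% of 3- to 7-day courses. And a patient on maintenance steroid shows that dose rather than zero. These points stand too.

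A reader might infer more than the documents support:
- *That average steroid dose is understated.* It is not, under random timing. If courses tended to start at visits, the visit-day mean would err upwards.
- *That a difference between canakinumab and placebo is hidden.* The by-visit groups follow SAP 1.3, which in Epoch 2 sorts patients by flare and up-titration and in Epoch 3 by up-titration and cumulative dose. The table does not compare randomised arms, and nothing documents more missed courses on placebo.
- *That dropped courses distort the Week 16 reduction test.* A rescue course that ended before Week 16 should not count towards a Week 16 maintenance dose. The risk runs the other way, from rescue that is included.

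**Conclusion.** The point holds in a limited form. As written, the by-visit steroid summaries do not show rescue courses falling wholly between visits. Under the two stated assumptions this is most short courses: about 69% to 96% of those lasting 1 to 7 days in Epoch 2, and about 87% to 98% at 56-day spacing. These percentages are not documented figures, and they shrink if courses are longer or rescue tends to begin at a visit. The mechanism itself needs no assumption.

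The loss is in the number of patients needing rescue in each interval, the timing of that need, and some precision. Mean dose, any-use counts, by-epoch counts and the confirmatory tests are unaffected. The mixing of maintenance and rescue doses in the Week 16 reduction analysis is a separate possible error, conditional on the mapped doses being used there. Both concern exploratory outputs, so this is a low-priority improvement that is worth making because it is cheap.

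**What to change.** 1. From the recorded start and end dates, report for each interval between visits: any steroid rescue (yes/no), days of use, and cumulative dose or cumulative dose divided by days in the interval. Present these by initial randomised treatment as well as by the SAP 1.3 groups. The visit-day table can stay, labelled as the dose on the day of the visit.
2. For the Week 16 reduction analysis, derive the maintenance dose at baseline and Week 16 apart from rescue courses, and state the rule that separates them.
3. State whether start and end dates count as inside a course, whether unscheduled visits receive a mapped dose, and whether the count of patients above 0.2 mg/kg/day uses mapped or course-level doses.

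The cost is a small programming change and a few sentences in the SAP. The mapping already uses the needed dates and doses, so no new data are collected.

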³ Only applicable for pediatric patients

⁴ The AIDAI and PPGA will be completed by the patient on an electronically diary daily from Screening till TD or PSW

⁵ Applicable for patients whose index flare has not resolved by Day 15. Blinded-escape add-on treatment may be initiated from Day 8 to Day 28

⁶ Applicable for patients on randomized treatment who flare on/ after Day 29 or patients on blinded-escape who will still have “mild”, “moderate” or “severe” disease activity (PGA ≥ 2 [clinical flare] and CRP ≥ 30 mg/L [serological flare]) or re-flare

Table 6-2 **Assessment schedule:**
Randomized withdrawal epoch (Epoch 3) and open-label treatment epoch (Epoch 4)

TD = Investigational treatment discontinuation

PSW = Premature subject withdrawal

X = assessment to be recorded on clinical data base

S = assessment to be recorded on source documentation

*These assessments are also to be conducted for patients who discontinue

#These assessments are source documentation only and will not be entered into the CRF

¹ To be performed 30 days following TD or PSW, or 8 weeks after last injection of investigational drug, whichever is later

² Only applicable for TRAPS patients rolling-over from CACZ885D2203/ CACZ885D2207M i.e. patients directly entering Epoch 3 following screening

³ Only applicable for pediatric patients

⁴ The AIDAI and PPGA will be completed by the patient on an electronically diary daily till Day 281 or PSW

⁵ Patients up-titrated to q4w administration in Epoch 4, will come back every 4 weeks for unscheduled visits at Day 309, Day 365, Day 421, Day 477, Day 533, Day 589, Day 645, Day 701 and Day 757 in addition to the scheduled visits

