Symptoms evaluated in the AIDAI diary will be summarized with each cohort and epoch.

Time to first new flare in the randomized withdrawal epoch (Epoch 3)

The two treatment groups (150 mg q8w and placebo) will be compared using a one-sided log-rank test at the 2.5% significance level. The hazard ratio and its associated 95% two-sided confidence intervals will be estimated. Kaplan-Meier estimates of the probability to experience a flare event will be calculated from the start of the randomized withdrawal epoch. 95% confidence intervals using Greenwood's formula will be provided.

SF-12 Health Survey (SF-12)

SF-12 scores will be summarized by epoch, visit and treatment arms within each cohort. Only patients ≥ 18 years of age at baseline will be part of the analyses.

Child Health Questionnaire – Parent Form 50 (CHQ-PF50)

Descriptive statistics will be used to summarize patient responses on the CHQ-PF50® Questionnaire by epoch, treatment, total score and by domain within each cohort. Only patients >5 - <18 years of age at Baseline are included.

Sheehan Disability Scale (SDS v3)

SDS score by domains and global functional impairment score will be summarized by epoch, visit and treatment arms within each cohort.

Number of flares

The number of flares by patient will be summarized by epoch and treatment arms within each cohort.

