1.5 Patient demographics and other baseline characteristics

Summary statistics will be provided for demographic and baseline characteristics for the below treatment groups, and by epoch:

1. In Epoch 2, by initial randomized treatment arms (canakinumab 150mg sc q4w, placebo, all subjects) and according to treatment groups defined in [section 1.3](#)
2. In Epoch 3, according to treatment groups defined in [section 1.3](#)
3. In Epoch 4, according to treatment groups defined in [section 1.3](#)

Demographics for subgroup of patients coming from ACZ885D2203 and/or the subsequent Multiple Patient Program (MPP) treatment plan CACZ885D2207M enrolled in Epoch 3 as well as canakinumab naïve Japanese crFMF patients with non-exon 10 mutations and patients >28 days but <2 years old enrolled in Epoch 2, will be presented separately from the other patients who will be screened and randomized in Epoch 2.

The following common background and demographic variables will be presented:

Continuous variables:

- Age at Baseline
- Height at screening
- Weight at screening
- Body mass index (BMI) at screening
- Time since first symptoms (years)
- number of flares per year
- average duration of flare (days)
- local standardized CRP (mg/l) at baseline
- SAA (mg/l) at baseline

Categorical variables:

- Age categories ($\geq 2- < 4$, $\geq 4- < 6$, $\geq 6- < 12$, $\geq 12- < 18$, $\geq 18- < 65$, ≥ 65)
- Gender (Male/Female)
- Race (White, Black or African American, Asian, Native Hawaiian or other, Pacific Islander, Unknown, Other)
- Ethnicity (Hispanic or Latino, Not Hispanic or Latino, Unknown, Not reported)
- Prior use of any biologics (No/Yes)
- Prior use of Anakinra (No/Yes)
- Prior use of Tocilizumab (No/Yes)
- Prior use of Etanercept (No/Yes)
- Confirmed gene mutation (TNFRSF1A gene for TRAPS, MEFV gene exon 10 for crFMF, MVK gene for HIDS) (No/Yes)
- Active disease at maximum colchicine dose (for crFMF patients) (No/Yes)
- Intolerance to effective doses of colchicine (for crFMF patients) (No/Yes)

- Type of mutation (display the first 3 most common mutation types then the rest in “Other” category) and allele
- Physician’s global assessment of disease activity at baseline (None, Minimal, Mild, Moderate, Severe)

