SF-12 measurements consists of 12 questions over eight subscales (physical function, pain, general and mental health, vitality, social function, physical and emotional health). The subscales can be aggregated to derive a physical-component summary score (PCS) and a mental-component summary score (MCS).

The score will be summarized for each subscale and for PCS and MCS.

Child Health Questionnaire – Parent Form 50 (CHQ-PF50)

Descriptive statistics will be used to summarize patient responses on the CHQ-PF50[®] Questionnaire by epoch (2 and 3), analysis visit, initial randomized treatment and treatment sequence (as defined in [section 1.3](#)), total score (Physical (PhS) and Psychosocial

(PsS) scores) and by domain within each cohort. Only patients $>5 <18$ years of age at baseline are included.

Sheehan Disability Scale (SDS v3)

SDS score by domain and global functional impairment score will be summarized by epoch (2 and 3), analysis visit, initial randomized treatment and treatment sequence (as defined in [section 1.3](#)) within each cohort.

Number of flares

The number of new flares by patient will be summarized by epoch and treatment arms within each cohort.

Disease-associated genetic mutations

Relationships between disease-associated genetic mutations and CRP/SAA/PGA values at Day 15 on patients randomized to Canakinumab will be analyzed by cohort. T-test will be used for mean comparison between genetic mutations for CRP and SAA, and wilcoxon rank sum test will be used for mean comparison between genetic mutations for PGA. Mean CRP, SAA, PGA at Day 15 were compared between

For cr-FMF cohort

- (i) all M694V gene vs overall cr-FMF canakinumab treated patients
- (ii) all M694V gene vs non-M694V gene
- (iii) M694V heterozygous vs homozygous

For HIDS cohort

- (i) all V377I gene vs overall HIDS canakinumab treated patients
- (ii) all V377I gene vs non-V377I gene
- (iii) V377I heterozygous vs homozygous

For TRAPS cohort

- (i) all R92Q gene vs overall TRAPS canakinumab treated patients
- (ii) all R92Q gene vs non-R92Q gene
- (iii) R92Q heterozygous vs homozygous

In the T-test procedure, Pooled and Satterthwaite methods for the p-value were used depending on the test on equality of variances.

In the Npar1way procedure, p-value from Exact test was taken given the relatively small sample size of patients.

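### Flares and diary fever episodes are tabulated as raw counts per epoch, with no allowance for time observed, and the documents disagree on when the fever diary ends

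*SAP*

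**What the plan says.** **Flares.** SAP 1.10.5: "The number of new flares by patient will be summarized by epoch and treatment arms within each cohort". Protocol 9.5.2 is almost identical: "The number of flares by patient will be summarized by epoch and treatment arms within each cohort". The related objective in protocol 2.3 is the number of flares by patient and by epoch.

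**Fever.** SAP 1.10.5: "Number and duration of fever episodes collected in patient's diaries will be summarized within each cohort, epoch and treatment group". It adds: "Plots of fever episodes per patient over time (displaying frequency and duration) and treatment group will also be presented".

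Neither variable has a rate, an offset or a rule for incomplete follow-up. SAP 1.13.1 does plan exposure-adjusted incidence rates by epoch, but for adverse events.

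**Columns.** SAP 1.3 displays Epoch 4 efficacy by cumulative dose over 72 weeks (below 2700 mg, 2700 to below 5400 mg, 5400 mg or more). In Epoch 3, patients who are not re-randomized or who are up-titrated are grouped by cumulative dose over 24 weeks, with cut-offs at 600 and 1200 mg.

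**Diary.** Fever is the first AIDAI item (protocol 6.4.6). Footnote 4 of protocol Table 6-2 says the AIDAI and PPGA "will be completed by the patient on an electronically diary daily till Day 281 or PSW". Protocol 6.4.6 and 6.4.7 give daily completion from screening until treatment discontinuation or premature withdrawal (TD/PSW), with no Day 281 limit. SAP 1.10.5 restricts the AIDAI summary to Epochs 2 and 3. SAP Table 1-2 leaves the AIDAI blank for Epoch 4 but marks Fever and PPGA there.

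**The concern.** A count depends on the event rate and on the time watched. Here the time differs by design between epochs and by early leaving between patients. Someone reading the tables from left to right would see counts rise with epoch length even if disease control did not change. Within an epoch, a group that loses patients early shows fewer flares for that reason alone. Where columns are defined by cumulative dose, leaving early also lowers the dose, so short follow-up and low dose collect in the same column.

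The diary question matters because a fever count has meaning only over days on which the diary was kept. The SAP gives no rule for absent diary days, and the documents do not agree on whether Epoch 4 has any diary days.

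**Working it through.** 1. **Epoch lengths, reproduced from visit days 1, 113, 281 and 785.** (113 − 1)/7 = 16 weeks; (281 − 113)/7 = 24; (785 − 281)/7 = 72. These match the stated lengths.

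2. **Nominal count ratios at a constant rate.** Expected count = rate × time, so count ratios equal time ratios: 24/16 = 1.5, 72/16 = 4.5, 72/24 = 3.0.

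3. **Risk window for new flares in Epoch 2.** Counting starts at Day 15 (protocol glossary) or Day 16 (protocol 6.4.5) if the index flare resolved at Day 15, and otherwise at Day 29.
   - From Day 15: (113 − 15)/7 = 14 weeks; 72/14 = 5.1.
   - From Day 16: (113 − 16)/7 = 13.9 weeks; 72/13.9 = 5.2.
   - From Day 29: (113 − 29)/7 = 12 weeks; 72/12 = 6.0.
   
   Epoch 4 to Epoch 2 is therefore about 5.1 to 6.0 for new flares. Epoch 3 to Epoch 2 is 24/14 = 1.7 to 24/12 = 2.0.

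4. **Illustration.** Assume 12 flares per year throughout. This is the crFMF entry criterion of at least one attack per month, a pre-study frequency and not a forecast on treatment. With 52.18 weeks per year:
   - Epoch 2, nominal: 12 × 16/52.18 = 3.68. With the new-flare window: 12 × 14/52.18 = 3.22 or 12 × 12/52.18 = 2.76.
   - Epoch 3: 12 × 24/52.18 = 5.52.
   - Epoch 4: 12 × 72/52.18 = 16.56.
   
   The rate is 12 per patient-year in every row.

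5. **Early leaving.** The documents give no dropout figure. If a share f leaves at mid-epoch (assumed), the mean count is multiplied by 1 − f/2: 0.95 at 10%, 0.90 at 20%, 0.85 at 30%. A rate per patient-year is unaffected if the flare rate is constant and unrelated to leaving.

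6. **Movement between cumulative-dose columns** (patients over 40 kg; no dose counted at the closing visit, as in the SAP's Epoch 3 example).
   - Epoch 4 with full follow-up: 150 mg q4w gives 18 × 150 = 2700 mg, 300 mg q8w gives 9 × 300 = 2700 mg, and 300 mg q4w gives 18 × 300 = 5400 mg. Each total sits exactly on a cut-off, so one dose fewer moves the patient down a column.
   - A patient on 300 mg q4w who leaves before the ninth dose (week 32) has at most 8 × 300 = 2400 mg. That patient joins the column SAP 1.3 describes as patients starting on 150 mg q8w.
   - Epoch 3: a patient on 300 mg q8w who leaves before the second dose at Day 169 has 300 mg and falls below 600 mg. Full follow-up gives 3 × 300 = 900 mg.

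7. **Diary days in Epoch 4.** 785 − 281 = 504 days. If the Table 6-2 footnote governs, none of the 504 has a diary entry. If sections 6.4.6 and 6.4.7 govern, up to 504 do.

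**The case against.** The case for leaving the plan alone has several parts.

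- **No between-epoch comparison is planned.** Number of flares is an exploratory summary shown separately for epochs of known length. This is correct and limits the importance of the point. A reader might infer that the plan would report a false 4.5-fold difference. It makes no such comparison, and 4.5 is only the nominal ratio of Epoch 4 to Epoch 2 with full follow-up.
- **Arms within an epoch share a nominal length.** This holds for the randomized columns, where distortion needs unequal early leaving. It does not hold for the cumulative-dose columns, where early leaving helps to decide the column.
- **A rate does not make every column comparable.** Epoch 2 columns are partly defined by whether a flare occurred, and flares raise cumulative dose in Epochs 3 and 4. Scheduled visits are 4 weeks apart after Day 29 in Epoch 2 but 8 weeks apart in Epochs 3 and 4. Person-time removes only the part due to unequal follow-up.
- **Follow-up is visible elsewhere.** SAP 1.6 and 1.8 report disposition and duration of exposure. Time to first new flare in Epoch 3 has Kaplan-Meier and log-rank analyses with a rule for discontinuation, and fever episodes are plotted over time. These help, but they do not put a denominator under the counts.
- **The diary may run through Epoch 4.** A reader of the footnote alone might infer that Epoch 4 diary fever is empty by construction and would be reported as zero. The documents do not support that. Protocol 6.4.6 and 6.4.7 and SAP Table 1-2 point the other way, fever is also assessed through body temperature at visits (protocol 6.4.2), and SAP 1.1 reports the number of patients with non-missing data for continuous summaries. The footnote and the AIDAI restriction support a Day 281 stop, so this is a contradiction and not an established gap.

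**Conclusion.** The point holds as a minor improvement to exploratory reporting. Flare and diary-fever counts have no denominator, although time observed differs by design. At a constant rate and full follow-up, counts run 1 : 1.5 : 4.5 by nominal length, and about 5.1 to 6.0 for new flares in Epoch 4 against Epoch 2. Early leavers have truncated counts and can fall into lower-dose columns in Epochs 3 and 4. How far this would distort any table depends on dropout, which the documents do not give. The column argument assumes that flare counts follow the SAP 1.3 display, since the flare paragraph itself says only treatment arms. No primary or secondary conclusion is affected.

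The end of the diary is a separate inconsistency. The text alone does not settle which passage governs.

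**What to change.** **Rates.** Keep the counts and add, by epoch and group:
- new flares per patient-year at risk, with the risk window defined for each epoch (in Epoch 2 from Day 15/16 or Day 29, choosing between Day 15 and Day 16) and ending at the epoch's last visit or withdrawal;
- diary fever episodes per completed diary day, or per patient-year of completed diary.

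State that both remain descriptive and exploratory.

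**Diary.** Reconcile the Table 6-2 footnote, protocol 6.4.6 and 6.4.7, and the SAP's AIDAI, Fever and PPGA entries. If Day 281 governs, remove diary fever and diary PPGA from Epoch 4 in Table 1-2, or label Epoch 4 fever as visit body temperature. If TD/PSW governs, correct the footnote, keep the entries and explain why the AIDAI summary stops at Epoch 3. Either way, treat absent diary days as missing and not as zero.

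**Baseline history.** SAP 1.5 summarizes "number of flares per year" at baseline. If on-study rates are shown beside it, add a note that definition and ascertainment may differ: on-study flares need PGA ≥2 together with CRP ≥30 mg/L, and the documents do not say that the history item used that rule.

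**Cost.** SAP wording, a denominator for each variable and one clarification of the diary end. No new data are needed: visit dates and diary entries are already collected, and the SAP already plans exposure-adjusted rates for adverse events.
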